3.2 Measurements of Outcomes

Primary Outcome Measure:

1. Progression of oxygenation needs

Count of participants initially presenting with mild/moderate disease who progress to requiring advanced oxygenation (high flow nasal canula, non-rebreather, continuous positive airway pressure (CPAP), bilevel positive airway pressure (BIPAP), or intubation)

[Time Frame: up to 1 month]

Secondary Outcome Measure:

2. Renal failure

Count of participants who develop or experience worsened renal failure as defined by RIFLE criteria, a 5-point scale where the categories are labeled: Risk-Injury-Failure-Loss-End stage renal disease, with Risk being the least severe and End stage renal disease being the most severe. The criteria for determination of stage are factors of serum creatinine and urine output. Numbers of participants worsening one or more RIFLE stages will be reported.

[Time Frame: up to 1 month]

3. Liver failure

Count of participants who develop or experience worsened liver failure as defined by serum transaminases five times normal limits

[Time Frame: Daily times 5, then weekly]

4. Cytokine Storm

Count of participants who develop cytokine storm as measured by elevated markers of inflammation (elevated D-dimer, hypofibrinogenemia, hyperferritinemia), evidence of acute respiratory distress syndrome (ARDS) measured by imaging findings and mechanical ventilator requirements, and/or continuous fever (≥ 38.1 ° Celsius unremitting)

[Time Frame: 1 month]

5. Mortality

Count of participants who die from COVID-19

[Time Frame: up to 1 month post hospital discharge]

6. Length of hospital stay

Length of hospital stay in days

[Time Frame: 1 month]

7. Intensive Care Unit (ICU) admission

Count of patients admitted to the ICU at any time during index hospitalization

[Time Frame: 1 month]

8. Intensive Care Unit (ICU) duration

Length of ICU stay in days

[Time Frame: 1 month]

9. Intubation

Count of participants requiring intubation

[Time Frame: 1 month]

10. Intubation duration

Length of intubation, measured in days

[Time Frame: 1 month]

11. Time until recovery

Time measured in days from hospital admission to determination patient is stable for discharge

[Time Frame: 1 month post hospital discharge.]

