If at any point a patient requires advanced oxygenation (hiflo nasal cannula, non-rebreather, CPAP, BIPAP, or intubation) for more than 15 minutes they will then be given ketamine as a rescue treatment and remain on the Naltrexone or placebo. Ketamine will initially be given at a dose of 0.15 mg/kg based on total body weight (max 20 mg) every 6 hours (+/- 1 hour) by intravenous piggyback over 30 minutes. Ketamine will continue until the patient is deemed stable for low level oxygen. If the patient relapses after the ketamine is stopped they can be restarted on the ketamine. If the patient continues to worsen or displays evidence of cytokine storm (elevated markers of inflammation, evidence of ARDS, continuous fever) the dose of ketamine will be increased to 0.3 mg/kg IV every 6 hours (max 30 mg). The dose of ketamine can be reduced back to 0.15 mg/kg at the clinical decision of the physician investigators. If a patient has issues with hypertensive emergency the dose of ketamine can be held until the hypertensive emergency is controlled.

In addition, a patient can receive ketamine if they are not yet on advanced oxygenation if the investigating physician feels they are moving toward cytokine storm based on the markers of inflammation and clinical factors such as worsening imaging and unrelenting fever. If a patient transitions to comfort care the patient will remain in the study for data collection purposes. Study medications may be held if requested by the clinical team, patient, LAR or family.

Patients who at screening are already requiring advanced oxygen can be consented and enrolled in the study and immediately will skip the randomization and be placed on naltrexone and receive ketamine as the starting treatment in an open label manner.

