3.2 Statistical Analysis

Descriptive statistics will be provided for all variables collected including patient demographics, numbers progressing to requiring more oxygen, and all secondary outcomes. Categorical variables will be summarized as counts and percentages. All continuous variables will be summarized as means \pm the standard deviation where normal or median and 25th, 75th percentiles if not normal. The minimum and maximum will also be provided.

Analysis Sets: Data analysis will be performed on a full analysis set (FAS), a per protocol set (PPS), an intent-to-treat (ITT) set, and a safety analysis (SA) set.

The FAS will be used for the primary analysis. The FAS will consist of all randomized subjects who receive at least one naltrexone/placebo treatment. All analyses using the FAS will group participants according to randomized treatment in an intent-to-treat analysis.

The PPS will be used for a supportive analysis and will be defined as all subjects included in the FAS who do not have any significant protocol deviations. All analyses using the PPS will group subjects according to treatment the subject actually received.

The safety data set will include all subjects with all safety data but will lack any outcome data. This data set will be used for reporting to the internal safety committee.

Missing Data: We will evaluate the potential impact of any missing data on analyses before deciding how to include missing data. Missing data will not be replaced by substitutions or imputation as long as the percent missing for any of the variables is less than 5%. Should the percent missing increase above 5%, we will use multiple imputation to replace missing data and conduct any analyses outlined below.

Primary Outcome: Progression to requiring more oxygen will be the primary outcome, and we will compare the percent patients progressing between the two arms of this study. The primary hypothesis is that the percent progressing for those in the naltrexone arm will be less than the percent progressing in the placebo arm. We will use the Pearson chi-squared test this hypothesis using a one-sided type 1 error rate of 0.05. We will also estimate the difference in proportion progressing using a Bayesian approach with independent Jeffrey's priors for both groups and numerical integration to obtain the credibility interval for the difference in proportions.

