Sample Size Determination: We assumed that 20% of patients admitted to the hospital will show progression to requiring more oxygen, and that we want to detect if naltrexone reduces the progression rate to no more than 10%. With these assumptions, a sample size of 154 per arm (308 total) is required to have 80% power based on a two-sample t-test, using PASS 16.

Secondary Outcomes: To examine the potential impact of ketamine on mortality, we will use the chi-squared test to evaluate the hypothesis that mortality is reduced in the naltrexone arm. We will also estimate the difference in proportions using the Bayesian approach noted above. We will use a type 1 error rate of 0.05 for this secondary outcome.

For all remaining secondary outcomes, we will estimate the difference between the two arms and not test for differences between the two arms since these data will be used in planning future studies. For dichotomous outcomes (renal failure, liver failure, cytokine storm, and ARDS), we will use the Bayesian approach discussed for estimating the difference in proportions. We will use generalized linear models to estimate the difference in durations (number of days in ICU, number of days on a ventilator, and length of stay), evaluating the distribution to use based on the data. We will consider using the Poisson, negative-binomial, and normal distributions. We will use a Bayesian approach, using a flat prior on the difference in means parameter. We will calculate 99% credibility intervals for all of these secondary outcomes given the multiple outcomes being examined.

For statistical analysis the biostatisticians and Data analytics teams at Beaumont ([name] and [name]) will pull patients who were not on SINK, had COVID-19 with as close to a direct match to patients with similar profiles who were treated on the SINK study. The match to the patients on SINK will aim to compare the outcomes of the two groups, to see if there is a difference in the outcomes. The evaluation is a chart analysis aimed at focusing on the outcomes of the study.

Safety Measures:

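### Apart from the COVID-19 mortality outcome, the plan has no rule for how death enters the primary outcome, the durations or time until recovery; the effect cannot be sized and may be small

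*Combined protocol and SAP*

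**What the plan says.** **Primary outcome.** 3.2 Measurements of Outcomes defines it as the "Count of participants initially presenting with mild/moderate disease who progress to requiring advanced oxygenation", over up to 1 month. Under 3.2 Statistical Analysis the hypothesis is that "the percent progressing for those in the naltrexone arm will be less than the percent progressing in the placebo arm". It is tested by Pearson chi-squared at one-sided 0.05 in the full analysis set, with 154 per arm planned.

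**Mortality.** It is a separate secondary outcome, "Count of participants who die from COVID-19", with its own chi-squared test between arms.

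**Durations.** The Secondary Outcomes paragraph reads "We will use generalized linear models to estimate the difference in durations (number of days in ICU, number of days on a ventilator", and its list ends with length of stay. On the distribution it says "We will consider using the Poisson, negative-binomial, and normal distributions". These outcomes are estimated with 99% credibility intervals, not tested, and are meant for planning later studies.

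**Time until recovery.** It is defined as "Time measured in days from hospital admission to determination patient is stable for discharge". It does not appear among the modeled durations.

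**Missing data.** The paragraph first promises to assess the impact of missing values, then sets a threshold: "Should the percent missing increase above 5%, we will use multiple imputation to replace missing data". Death is not mentioned.

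**Comfort care.** 3.1 Research Design says "If a patient transitions to comfort care the patient will remain in the study for data collection purposes". It does not say how such a patient is scored.

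**The concern.** A patient who dies leaves hospital, the ICU and the ventilator, and can no longer progress in oxygen need. Each of these outcomes therefore needs a rule for death, and none is given.

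- **Primary outcome.** A death without advanced oxygenation can receive the same score as a recovery. The abstractor must decide whether a comfort-care patient who declined escalation was *requiring* it.
- **Durations.** An early death gives a small number of days, which reads as a good result. The arm with more early deaths can look better.
- **Time until recovery.** A patient who dies in hospital never reaches the defined end point. If the blank were handled as missing, the 5% rule could drop it or impute a recovery time.

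At stake are the meaning of the primary result if such deaths differ between arms, and the direction of the duration estimates that are to feed later trials.

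**Working it through.** **Inputs from the documents.** 154 per arm, 308 in total; 20% versus 10% progression; one-sided 0.05 (3.2 Statistical Analysis). Two loose anchors for mortality: 20% × 20% = 4% reaching stage 3 (section 1.4) and 9.3% for Italy (section 1.1). Neither is a death rate for this inpatient population. **Assumptions:** every rate of death without advanced oxygenation, every time of death, and a 12-day stay for survivors.

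**1. The plan's own figure.** Unpooled normal formula: (1.645 + 0.842)² × (0.20×0.80 + 0.10×0.90) / 0.10² = 154.6, against the stated 154. The exact binomial power of the uncorrected one-sided chi-squared (pooled z) test at 154 per arm is 80.1%. The sample size reproduces.

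**2. Primary outcome under unequal uncounted deaths.** Suppose progression-or-death is truly 20% in both arms, and a net share q of one arm dies without being counted. The test then sees 20% − q in that arm. Exact chance of declaring benefit:

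| q | uncounted on naltrexone | uncounted on placebo |
|---|---|---|
| 0.5% | 6.3% | 4.0% |
| 1% | 7.8% | 3.1% |
| 2% | 11.6% | 1.8% |

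Equal uncounted deaths (19% vs 19%, or 18% vs 18%) leave it at 5.0%.

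**3. How many deaths would overturn the planned result.** The planned effect is about 31 versus 15 events of 154. Pooled proportion 46/308 = 0.149; z = (16/154) / √(0.149 × 0.851 × 2/154) = 2.56; p = 0.005. Adding deaths to the naltrexone count only: 31 vs 20 gives p = 0.046, and 31 vs 21 gives p = 0.064. So 6 net uncounted naltrexone deaths are needed to lose significance on progression-or-death.

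**4. Hospital stay.** Mean stay = (1 − m) × 12 + m × d, with mortality m and death at day d. Days alive and out of hospital to day 30, taking randomization as the admission day and scoring the dead 0, = (1 − m) × 18.

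| Mortality, worse vs better arm | Stay, d = 7 | Better minus worse, d = 7 | d = 12 | d = 15 | Days alive and out, better minus worse |
|---|---|---|---|---|---|
| 4% vs 2% | 11.80 vs 11.90 | +0.10 | 0 | −0.06 | +0.36 (17.28 to 17.64) |
| 9.3% vs 4.65% | 11.54 vs 11.77 | +0.23 | 0 | −0.14 | +0.84 (16.33 to 17.16) |
| 20% vs 10% | 11.0 vs 11.5 | +0.50 | 0 | −0.30 | +1.80 (14.4 to 16.2) |

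With early deaths, raw stay points against the better arm. Days alive points toward it.

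**5. Scale against the interval.** The 99% half-width for a difference in mean stay is 2.576 × SD × √(2/154). For an assumed SD of 4, 6 or 8 days this is 1.2, 1.8 or 2.3 days. The 0.1 to 0.5 day artefact lies inside it.

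**6. Time until recovery.** 5% of 308 = 15.4, so 16 or more blanks would pass the imputation threshold, provided that in-hospital deaths were treated as missing. The plan does not say that they would be.

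**The case against.** The strongest case is that the primary outcome does what it sets out to do. Aim 1.1, the outcome definition and the hypothesis all concern progression in oxygen need. A reader might infer from the 6.3% to 11.6% figures that the primary test has an inflated type 1 error. The documents do not support that. In those scenarios oxygen progression really is lower on naltrexone, so rejecting the stated hypothesis is correct. The figures are error rates only for progression-or-death, which the plan does not test. This part of the objection stands in full.

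A reader might also infer that every death without advanced oxygenation is scored as a recovery. The word *requiring* leaves room to count a comfort-care patient in respiratory failure as progressed. The gap is an unstated rule, not a proven misclassification. Nor do the documents say that recovery times will be imputed for the dead. That needs the unstated step of calling death missing, and the plan promises to assess the impact of missing data first.

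The impact may well be low. The event already includes high-flow cannula and non-rebreather, so many deaths may already follow a counted event. Mortality has its own between-arm comparison, so an excess of COVID-19 deaths would be visible beside the primary result. That reassurance is partial. Deaths from other causes are outside that outcome, and the test is weak: at 4% versus 2% with 154 per arm, exact power is 29% one-sided or 16% two-sided. It also does not rescore the durations.

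**Conclusion.** The omission is certain from the text; its size is not. Outside the COVID-19 mortality outcome, nothing says how death is scored.

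- **Durations.** This is the firmest part. Followed as written, the raw-day models can favor the arm with more early deaths. The illustrated artefact is 0.1 to 0.5 day and rests on an assumed 12-day survivor stay and deaths at day 7. It is zero for deaths at day 12 and reverses after that. It would not be distinguishable within the planned 99% interval.
- **Primary outcome.** The scoring of death without advanced oxygenation is open, but the test is valid for its own hypothesis. The documents give no rate for such deaths. If they are balanced between arms, the chance of falsely declaring benefit stays at 5%. It would be going too far to conclude that the endpoint must be replaced; a pre-specified progression-or-death analysis closes the gap.
- **Time until recovery.** It is undefined for an in-hospital death and has no named method.

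This should be fixed, with medium confidence that it would matter in practice.

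**What to change.** These changes affect scoring only, not clinical management.

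1. **Primary outcome.** Before unblinding, state how a death without advanced oxygenation is scored, including after comfort care. Pre-specify advanced oxygenation or death from any cause within 1 month of randomization as a key sensitivity analysis. If the sponsor prefers, make it the primary outcome with oxygenation-only as supportive, and restate power. Exact power at 154 per arm goes from 80% to 78% (21% vs 11%) or 76% (22% vs 12%), and would be 84% at 22% vs 11%. By the pooled normal formula, which gives 157 per arm at 20% vs 10%, keeping 80% would need 166 or 174 per arm in the first two cases.
2. **Durations.** Make the main estimates days alive and free of ICU, ventilator and hospital to day 30, scoring 0 if dead by day 30. Report a difference in means with a 99% interval from a bootstrap or an unequal-variance normal model. A Poisson model does not suit this score: at 4% mortality and an assumed survivor SD of 6, the variance is 0.96 × (6² + 18²) − 17.28² = 47, against a mean of 17.3. Show raw durations descriptively by survival status.
3. **Time until recovery.** Use cumulative incidence with death as a competing event. Reconcile the horizon with the stated time frame, which runs to 1 month after discharge although the measure starts at admission.
4. **Missing data.** State that death is not missing data under the 5% rule, and record deaths from any cause.

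**Cost.** Protocol and SAP wording and slightly more analysis. Oxygen need, ICU status and mortality are already abstracted daily (3.1 Research Design). Non-COVID-19 deaths and readmissions must be added at the existing weekly calls. Days-alive scores are also more variable than raw stay: in the 20% vs 10% case with survivor SD 6, the arm variances are 80.6 and 61.6, so the 99% half-width is 2.576 × √(142.2/154) = 2.5 days. The gain is in direction, not precision.

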After discharge patients will be called once a week (+/- 3 days) for 1 month to determine their current health status and review their medication compliance. If at the 1 month mark the patient has not resolved their symptoms fully the calls will be extended for an additional month, once a week.

While the exact time the patient will remain in the study is unclear depending on duration of the admission and duration of symptoms, we expect it will be approximately 3 months on average.

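### Mortality, the only tested secondary outcome, is limited to deaths from COVID-19 without an attribution rule; the test should use death from any cause

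*Combined protocol and SAP*

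**What the plan says.** Section 3.2 Measurements of Outcomes, item 5, defines mortality as "Count of participants who die from COVID-19", observed "up to 1 month post hospital discharge". Section 3.2 Statistical Analysis (Secondary Outcomes) says "we will use the chi-squared test to evaluate the hypothesis that mortality is reduced in the naltrexone arm", with a Bayesian interval for the difference in proportions alongside, and adds: "We will use a type 1 error rate of 0.05 for this secondary outcome". It does not say whether that 0.05 is one-sided or two-sided; only the primary test is declared one-sided. (The same sentence introduces the test as a look at ketamine, which is a separate matter.)

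No other secondary outcome is tested: "For all remaining secondary outcomes, we will estimate the difference between the two arms and not test for differences between the two arms".

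Section 3.1 provides post-discharge follow-up: "After discharge patients will be called once a week (+/- 3 days) for 1 month", extended by a month if symptoms persist. Length of stay is itself compared between the arms, among the durations listed as "number of days in ICU, number of days on a ventilator, and length of stay".

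**The concern.** A count of deaths from one cause needs a decision on each death. The plan names no criteria, no adjudicator and no handling of deaths from other causes. The restriction to COVID-19 appears only in the outcome list, so two analysts could follow the text and test different sets of deaths.

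Under the restricted reading, any death put down to something else leaves the comparison. That includes a death that study treatment might have contributed to, which is a kind of death a mortality comparison ought to retain. Losing genuine disease deaths through misattribution also reduces an already small event count.

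A second, smaller issue is the window. It closes one month after discharge, so each survivor's observation time depends on length of stay, which follows randomisation and which treatment may change.

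**Working it through.** **1. The plan's own figure.** There is no sample-size or power figure for mortality. The 154 per arm belongs to the primary outcome (20% versus 10%, 80% power, one-sided 0.05). The unpooled formula gives (1.645 + 0.842)² × (0.2×0.8 + 0.1×0.9) / 0.1² = 154.6, so 155; the pooled formula gives 157. Both are close to the stated 154, which I use as the arm size below.

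**2. The texts side by side.**

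| Place | Wording on mortality |
|---|---|
| Aims 1.3 and 2.2 | unrestricted |
| 3.1, daily chart abstraction | unrestricted |
| 3.2 Measurements of Outcomes, item 5 | deaths from COVID-19 only |
| 3.2 Statistical Analysis, the test | unrestricted |

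None of these gives a rule for cause of death.

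**3. Power if deaths are excluded equally in both arms.** All mortality rates here are assumptions. With p̄ the mean of the two rates and n = 154:

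power = Φ[(p₁ − p₂ − 1.645·s₀) / s₁], where s₀ = √(2p̄(1−p̄)/n) and s₁ = √([p₁(1−p₁) + p₂(1−p₂)]/n).

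- 10% versus 5%, nothing excluded: s₀ = 0.03002, s₁ = 0.02988, (0.05 − 1.645×0.03002)/0.02988 = 0.02, power 0.51.
- 30% of deaths excluded in each arm (7% versus 3.5%): s₀ = 0.02542, s₁ = 0.02534, (0.035 − 1.645×0.02542)/0.02534 = −0.27, power 0.39.

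| Assumed all-cause rates | One-sided, 0% → 30% excluded | Two-sided, 0% → 30% excluded |
|---|---|---|
| 10% vs 5% | 0.51 → 0.39 | 0.38 → 0.28 |
| 15% vs 7.5% | 0.67 → 0.53 | 0.55 → 0.40 |
| 20% vs 10% | 0.79 → 0.64 | 0.69 → 0.52 |

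This supposes that the excluded deaths carry the same relative treatment effect as the rest, as happens when disease deaths are misattributed at random.

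**4. The window.** Observation time for a survivor is remaining stay plus about 30 days: 35 days for a 5-day stay, 40 for a 10-day stay. As an upper-end illustration, suppose an identical constant daily death hazard h in both arms and stays of 10 versus 5 days. The spurious difference is (1 − e^(−40h)) − (1 − e^(−35h)): 0.5 percentage points at h = 0.001 and 2.1 points at h = 0.005. A constant hazard probably overstates this, because it gives discharged survivors the same risk as inpatients. A COVID-19 death in hospital during the index stay counts however long the stay, so a shorter stay can lose only deaths later than one month after discharge.

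**5. Is a fixed day from randomisation observable?** Four weekly calls with a 3-day tolerance put the last at 28 ± 3, that is 25 to 31 days after discharge. Anyone discharged 5 or more days after randomisation is therefore covered to day 30 (5 + 25). Only an earlier discharge combined with an early last call leaves a gap, provided the calls are completed.

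**The case against.** A reader might infer that the definition favours naltrexone. The documents do not support that. The randomised comparison is double-blind, and patients who progress in either arm receive ketamine while staying on their blinded treatment, so open-label ketamine does not reveal allocation. Attribution errors should be mainly non-differential. If 20% of deaths were excluded in the naltrexone arm alone, with equal true mortality of 10% to 20%, one-sided rejection would rise from 0.05 to between 0.15 and 0.23, but nothing in the plan points to such an imbalance. Nor does anything suggest that organ-failure deaths would be called unrelated: the plan treats renal failure, liver failure and ARDS as outcomes of interest.

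It is also tempting to say that one attribution call could reverse the result. With 154 per arm, 15 versus 7 deaths gives one-sided p = 0.038 and 14 versus 7 gives 0.057. Two-sided, the same counts give 0.077 and 0.114, with no reversal. Any test near its threshold can turn on one event, so this is not evidence of bias.

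A further fair objection is that correct attribution can help power. If the excluded deaths were truly unrelated and equal in the arms, say 3 points out of 10% versus 5%, the comparison becomes 7% versus 2%: s₀ = 0.0236, s₁ = 0.0235, (0.05 − 1.645×0.0236)/0.0235 = 0.47, power 0.68 instead of 0.51. That stands, but it presupposes reliable attribution, which the plan does not provide for.

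Finally, the present window matches treatment, which runs to 30 days past discharge. Replacing it with day 30 from randomisation would drop late in-hospital deaths from the test. That also stands, and is why the fixed day belongs in a supporting analysis.

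**Conclusion.** The point holds as a gap in the definition of the only tested secondary outcome. The outcome list restricts mortality to COVID-19 deaths, the rest of the plan does not, and no attribution rule connects the two. The expected consequences are lost power where disease deaths are misattributed, and possibly drug-related deaths missing from the tested comparison. A systematic advantage for one arm is not shown.

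The size cannot be computed from the documents. The fall in one-sided power from 0.51 to 0.39 rests on assumed rates of 10% and 5%, 154 per arm, and 30% of deaths excluded equally in both arms with the same relative effect. The dependence of the window on length of stay is real in principle but probably small, and does not by itself justify replacing the tested window.

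**What to change.** In 3.2 Measurements of Outcomes, define the tested mortality outcome as death from any cause, and use that definition in both the chi-squared test and the Bayesian interval. This also brings the outcome list into line with the Aims. Keep COVID-19-attributed death as a descriptive summary.

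Add one supporting analysis: death from any cause by a fixed time from randomisation, the same in both arms. The sponsor should choose the time from follow-up already planned. Day 30 is one example, which the existing calls nearly always cover; for patients discharged very soon after randomisation, placing the last call at or after that day closes the remaining gap.

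The cost is a wording change and one extra analysis, with essentially no new data. The downside is that all-cause death includes some deaths unrelated to the disease, which can dilute an effect. It is a cheap improvement.
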